8. INVESTIGATORS REGULATORY OBLIGATIONS

8.1 Pre-study Documentation

The Investigator must provide the Sponsor or designee with the following documents BEFORE consenting any patients:

1. All applicable regulatory forms
2. Current signed and dated curricula vitae for the Investigator, sub-Investigators, and all key personnel listed on the clinical study information form
3. Copy of the IRB approval letter for the protocol and informed consent
4. Copy of the IRB-approved ICF to be used
5. When applicable, a list of the IRB members and their qualifications, and a description of the committee's working procedure
6. Copy of the protocol signature page signed by the Investigator
7. Fully executed clinical study agreement (CSA)
8. Completed FDA Form 1572.

8.2 Electronic Data Capture

The CRO will supply the investigational site with access to a web based EDC computer system. Edit checks and data logic checks are at the point of entry and are validated according to company standard operating procedures. All data entered into the system are transferred to a secure database maintained by the CRO.

Access to the EDC system at the site, for vendors, at the Sponsor, and at the CRO is password protected. Study access is granted to site personnel only after they have been trained in the use of the EDC system by web based training at the investigational site.

The EDC system contains a system generated audit trail that captures any changes made to a data field, including who made the change, and the date and time it was made. This information is available at the Investigator's site, at the CRO, and at the Sponsor.

Data entries made in the EDC screens should be completed within 5 days of the patient's study visit and must be supported by source documents maintained for all patients enrolled in the study.

The data collection tool for this study will be the validated electronic system. Patient data necessary for analysis and reporting will be entered and transmitted via the electronic system. Clinical data management will be performed in accordance with applicable

standards and data cleaning procedures. For data coding (e.g., AEs, medication), internationally recognized and accepted dictionaries will be used.

At the conclusion of the study all data will be delivered to the Sponsor.

8.3 Adverse Event Reporting

The Investigator agrees to report all AEs to the Sponsor as described in Section 6.6.3.1. Furthermore, the Investigator is responsible for ensuring that any sub-Investigator promptly brings AEs to the attention of the Investigator. If applicable, the Investigator is also responsible for informing the site's IRB of all SAEs (per IRB requirements).

8.4 Review of Source Records

The Investigator agrees that the Study Monitor (and other qualified personnel as appropriate) will be allowed to conduct site visits to the investigational facilities for the purpose of reviewing source records pertinent to the study. The Investigator will make the study files available during monitoring visits. These files will also be available for inspection by representatives of the Sponsor, competent authorities and/or the IRB. Patients will not be identified by name on any of the study documents utilized by the Sponsor for their analysis, and confidentiality of information in medical records will be preserved. Every effort will be made to maintain the confidentiality of the patient unless disclosure is required by regulations.

8.5 Monitoring of the Study

The Study Monitor will be responsible for monitoring this clinical trial. The Study Monitor will monitor the study conduct, proper eCRF completion, source documentation completion and retention, and accurate study drug accountability. The Study Monitor will visit the study site at suitable intervals and be in frequent contact through verbal and written communication with the site. It is essential that the Study Monitor have access to all documents (related to the study and the individual participants) at any time these are requested. In turn, the Study Monitor will adhere to all requirements for patient confidentiality as outlined in the ICF. The Investigator and Investigator's staff will be expected to cooperate with the Study Monitor, to be available during a portion of the monitoring visits to answer questions, and to provide any missing information.

8.6 Protocol Amendments

Any substantial amendments in the research protocol during the period, for which the IRB approval had already been given, will not be initiated without submission of an amendment for IRB review and approval.

These requirements for approval will in no way prevent any immediate action from being taken by the Investigator in the interest of preserving the safety of all patients included in the trial.

8.7 Protocol Deviations

A protocol deviation is any departure from the defined procedures and treatment plans as outlined in the protocol version submitted and previously approved by the IRB. Protocol deviations have the potential to place participants at risk and can also undermine the scientific integrity of the study thus jeopardizing the justification for the research. Protocol deviations are unplanned and unintentional events.

Investigational sites will report protocol deviations to their IRB per institutional reporting requirements.

8.8 Change in Investigator

If any Investigator retires, relocates, or otherwise withdraws from conducting the study, the responsibility for maintaining records may be transferred to the Sponsor or designee, IRB, or another Investigator. The Sponsor or designee must be notified of and agree to the change. Regulatory agencies will be notified with the appropriate documentation.

8.9 Criteria for Termination of the Study or Study Center/Site

8.9.1 Early Termination of the Study

If the Sponsor or its designee, the Investigator or regulatory agency discovers any condition arising during the study that indicate that the study or the study site should be terminated, this action may be taken after appropriate consultation between the Sponsor or its designee and the Investigator. The Sponsor or its designee has the right to terminate the participation of either an individual site or the study at any time, for any reason which may include the following:

- The incidence and severity of AEs in this or other studies indicates a potential health hazard to patients.
- Patient enrollment is unsatisfactory.
- Data recording is inaccurate or incomplete.
- Investigator(s) do(es) not adhere to the protocol or applicable regulatory guidelines in conducting this study.
- Submission of knowingly false information from the study site to the Sponsor or its designee or regulatory authorities.

In the event that the study is terminated early, the Sponsor or its designee will provide specific guidance to investigational sites regarding the end of study procedures.

8.10 Clinical Study Report

A clinical study report (CSR) will be prepared following the completion of the study.

8.11 Confidentiality

All unpublished information that the Sponsor gives to the Investigator shall be kept confidential and shall not be published or disclosed to a third party without the prior written consent of the Sponsor.

When the Sponsor generates reports for presentations to regulatory agencies, one or more of the Investigators who has/have contributed significantly to the study may be asked to endorse the final report.

The Investigator shall not make a patent application based on the results of this study and shall not assist any third party in making such an application without the written authorization of the Sponsor unless otherwise specified in the CSA.

8.12 Records Retention

Essential documents must be retained for longer than 5 years after completion of the study, 2 years after the final marketing authorization in an ICH region or until at least 2 years have elapsed since the discontinuation of clinical development of the study drug. If it becomes necessary for the Sponsor or the Competent Authority to review any documentation relating to the study, the Investigator must permit access to such records.

Study files may be discarded upon written notification by the Sponsor. To avoid error, the Investigator must contact the Sponsor before destroying any records or reports pertaining to the study, to ensure that retention is no longer required. Other source documents, such as patient's medical records, must be retained for the maximum period of time permitted by the hospital or institution and until such time when the Investigator is informed by the Sponsor that there is no further need to do so.

In addition, in accordance with the Investigator agreement, the Sponsor should be contacted if the site's Principal Investigator plans to leave the investigational site so that appropriate arrangements can be made.

10. APPENDICES

APPENDIX A – Acute Myeloid Leukemia Response Criteria

The IWG consensus criteria for treatment response in AML will be used to evaluate response to treatment.

Definitions of Remission

Morphologic complete remission (CR): ANC >1000/ μ L, platelet count >100,000/ μ L, <5% bone marrow blasts, no Auer rods, no evidence of extramedullary disease.

Morphologic CR with incomplete blood count recovery (CRi): CRi, which is CR without recovery of neutrophils and/or platelets (ANC may be <1000 μ L and/or platelet count <100,000/ μ L).

Partial remission (PR): ANC >1000/ μ L, platelet count >100,000/ μ L and at least a 50% decrease in the percentage of marrow aspirate blasts to 5 to 25%, or marrow blasts <5% with persistent Auer rods.

Progressive Disease

Progressive disease (PD) is defined as any one of the following:

- More than 50% increase in bone marrow blast % from best assessment (with a minimum threshold of 20% blasts in the marrow).
- >50% increase in circulating malignant blasts (with absolute blasts >1000/ μ L).
- Development of biopsy-proven extramedullary leukemia (if the patient has extramedullary disease at baseline then PD will be defined by blood and marrow criteria or if new sites of extramedullary disease appear).

In patients who present with initial marrow blast percentage sufficiently high to preclude the ability to base disease progression on a >50% increase in marrow blast percentage; disease progression should be based on peripheral blood criteria or development of extramedullary leukemia.

Stable Disease

Patients who fail to achieve CR, CRi or PR and who do not have criteria for PD will be defined as having stable disease. If the patient dies prior to response assessment at the end of Cycle 1, then they will be classified as “Indeterminate”.

Relapse from CR or CRi

Reappearance of leukemia blasts in the peripheral blood; or >5% blasts in the bone marrow not attributable to another cause (e.g., recovery of normal cells following chemotherapy-induced aphasia); or appearance or reappearance of extramedullary disease and the bone marrow blast percentage is >5% but < or equal to 20%, than a repeat bone marrow performed at least 7 days after the first marrow examination and documenting bone marrow blast percentage is >5% is necessary to establish relapse.

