6.6.2 Efficacy Assessments

6.6.2.1 *Primary Efficacy Assessment*

The primary endpoint is the rate of patients in each treatment group achieving morphological CR based on IWG criteria during the induction and re-induction phases of the treatment. Morphologic CR is defined as ANC >1000/ μ L, platelet count >100,000/ μ L, <5% blasts in an bone marrow aspirate sample, no blasts with Auer rods, and no evidence of extramedullary disease (see Appendix A).

6.6.2.2 *Secondary Efficacy Assessments*

6.6.2.2.1 *Event-Free Survival*

Event-free survival is measured from the date of randomization until treatment failure (e.g., failure to achieve composite complete morphological remission during the induction or re-induction phase of the study lasting up to 60 days, relapse from CR, or death from any cause, whichever occurs first).

6.6.2.2.2 *Leukemia-Free Survival*

Leukemia-free survival is only assessed in patients who achieve composite CR and is measured from the date of randomization until disease relapse or patient death from any cause, whichever occurs first.

6.6.2.2.3 *Overall Survival*

Overall survival is measured from the date of randomization until death from any cause.

6.6.2.2.4 *Composite Complete Remission Rate*

Complete remission rate includes CR, CR without recovery of platelets (CRp) and CRi as defined by IWG criteria (Appendix A) during the induction and re-induction phases of treatment.

6.6.2.2.5 *Duration of Morphologic Complete Remission*

Duration of morphologic complete response is measured from the achievement of CR to detection of relapse.

6.6.2.2.6 *30-Day, 60-Day and 90-Day Mortality*

Thirty-day, 60-day, and 90-day mortality are the rate of death during 30 days, 60 days, and 90 days, respectively, from the first day of induction treatment.

6.6.2.2.7 *Neutrophil and Platelet Recovery*

Time to neutrophil recovery is measured from the date of randomization until ANC recovers to $>1000/\mu\text{L}$.

Time to transfusion-independent platelet recovery is measured from the date of randomization until the first day that the platelet count recovers to $>100,000/\mu\text{L}$ (provided it is not as a consequence of platelet transfusion and provided platelets are then maintained at $>100,000/\mu\text{L}$ for the five subsequent days without platelet transfusion).

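### Appendix A's relapse sentence has two conflicting readings and the SAP defines relapse differently for duration of CR, so one patient can relapse for one endpoint and not for another

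*Protocol*

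**What the plan says.** Protocol Appendix A, under relapse from CR or CRi, gives three routes in a single sentence. The first two are "Reappearance of leukemia blasts in the peripheral blood; or >5% blasts in the bone marrow not attributable to another cause". Each stands alone, and neither carries an upper blast limit or asks for a second sample. The third is "or appearance or reappearance of extramedullary disease and the bone marrow blast percentage is >5% but < or equal to 20" per cent. After a comma this continues with "than a repeat bone marrow performed at least 7 days after the first marrow examination", and that marrow, "documenting bone marrow blast percentage is >5% is necessary to establish relapse". Among other conditions, CR in the same appendix requires "no Auer rods, no evidence of extramedullary disease".

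Three secondary endpoints use relapse:

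- **LFS** (Protocol 6.6.2.2.2) "is measured from the date of randomization until disease relapse or patient death from any cause".
- **EFS** (6.6.2.2.1) counts relapse from CR as an event.
- **Duration of morphologic CR** (6.6.2.2.5) ends when relapse is detected.

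SAP 3.2 moves the LFS start date, and SAP section 8 declares that change. The SAP's EFS and LFS entries do not redefine relapse, so they appear to fall back on Appendix A.

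For duration of morphologic CR and of composite CR, SAP 3.2 does redefine it: relapse is progressive disease (PD), or death due to clinical progression. PD in Appendix A is any one of:

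- a marrow blast increase of more than 50% from best, with a floor of 20%;
- a rise of more than 50% in circulating blasts, with an absolute count above 1000/μL;
- biopsy-proven extramedullary leukemia (for patients who had it at baseline, only new sites count).

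SAP section 8 does not list the changed relapse definition.

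**The concern.** The relapse sentence appears to have run two rules together: that extramedullary disease is a form of relapse, and that a low-level marrow finding needs confirming. The word *than*, where *then* seems meant, suggests a lost sentence break, but nothing in the documents shows which reading was intended. Two sites or two programmers could therefore code the same patient differently.

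On the literal reading, a patient in remission who develops extramedullary disease with a clear marrow no longer meets CR and yet has not relapsed. That patient stays event-free for EFS and LFS until blood or marrow relapse, death or censoring. In other cases either the event or its date depends on which clause is applied. The trial is open-label. Confirmatory slides are requested only for documented CR, and neither schedule (Protocol Tables 6-1 and 6-2) lists a marrow to confirm a suspected relapse.

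**Working it through.** **1. The plan's own figure.** The only design calculation is the power of each one-sided Fisher exact test on CR (Protocol 6.8.1, SAP 2.6). Inputs: 25 per arm, 0.55 versus 0.80, alpha 0.15.

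Power = Σx Σy Bin(x; 25, 0.55) · Bin(y; 25, 0.80) · 1[one-sided Fisher p ≤ 0.15], over all 26 × 26 outcomes.

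The result is 71.7%, against 71.8% stated, so the figure reproduces. Its inputs are CR proportions only; relapse does not enter.

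**2. The definitions side by side.** All rows assume no blasts in blood. *Literal* ties extramedullary disease (EMD) to the >5-20% marrow and the repeat. *Split* ends the third route before *and*, so the repeat rule covers every >5-20% marrow.

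| Finding in a remitter | Appendix A, literal | Appendix A, split | SAP, duration of CR |
|---|---|---|---|
| EMD, marrow ≤5% | not relapse | relapse | relapse if biopsy-proven |
| Marrow >5-20%, no EMD, no repeat | relapse at once | conflict: immediate by the second route, unestablished by the last clause | not relapse below 20% |
| Marrow >5-20%, no EMD, repeat >5% | relapse at first marrow | relapse, date unstated | not relapse below 20% |
| Marrow >5-20% with EMD, no repeat | conflict: immediate and unestablished | relapse through EMD | relapse if biopsy-proven |
| Marrow >5-20% with EMD, repeat >5% | relapse, date unstated | relapse | relapse if biopsy-proven |
| Marrow >20% | relapse | relapse | relapse |

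In the last row, PD also needs the increase of more than 50%, read here as relative. A remitter's best marrow is below 5%, so a marrow above 20% is an increase of more than (20 − 5)/5 = 300%, and the condition is met.

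**3. What the table shows.**

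- *Literal:* the third route adds nothing, because any marrow that satisfies it already satisfies the second.
- *Split:* the extramedullary gap closes, but the conflict extends to every >5-20% marrow.
- *Either reading against the SAP:* a 12% marrow without EMD, confirmed by a repeat marrow that is also below 20%, is a relapse for EFS and LFS but not for duration of CR. That patient's remission continues past the date of the LFS relapse. On the literal reading, biopsy-proven isolated EMD goes the other way: it ends duration of CR but not LFS.
- Blood differs too. Any reappearance of leukemic blasts is relapse in Appendix A, whereas the PD blood criterion needs more than 1000/μL.

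**4. Scale per patient.** The planning rates give 25 × (0.55 + 0.80 + 0.80) = 13.75 + 20 + 20 = 53.75 expected morphologic CRs. LFS is assessed in composite-CR patients, so its denominator is at least this large under the same rates. One reclassified patient is then at most 1/13.75 = 7.3% of the control LFS set or 1/20 = 5.0% of a dose arm's, and 1/25 = 4.0% of an arm for EFS. How many patients would be reclassified cannot be derived from the documents.

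**5. Scale of the date shift.** Where the repeat rule applies, the two candidate event dates are at least 7 days apart.

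**The case against.** The best defence is that the sentence is a drafting slip with little consequence. Biopsy-proven extramedullary leukemia alone is PD, so such a case is classifiable and is an event for both duration-of-CR endpoints. EFS and LFS analyses are descriptive. Long-term relapse data are collected only every 3 months, and SAP 6.2 sets a missing day in a follow-up date to the 15th, which can itself move a date by up to 31 − 15 = 16 days. Beside that, a 7-day difference in a few patients is small.

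Most of this stands. The date shift alone would not justify the point, and the consequence is limited to secondary endpoints. A reader might also infer that isolated extramedullary relapse is never an event, and that every >5-20% marrow is at the same time an immediate and a pending relapse. The documents do not support that combination. The first part belongs to the literal reading and is limited to EFS and LFS. The second belongs to the split reading, under which isolated extramedullary disease does count. On the literal reading, a 12% marrow without extramedullary disease is simply an immediate relapse.

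What the defence does not answer is that no rule chooses between the readings, and that neither reading agrees with the SAP definition for duration of CR.

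**Conclusion.** The Appendix A sentence is defective on either reading, and the plan carries two relapse definitions without declaring it. The same patient can therefore relapse for one endpoint and not for another. This should be corrected, but it is not a threat to the main result. It reaches EFS, LFS and duration of morphologic and composite CR only. The primary endpoint, CR during induction and re-induction, and its 71.8% power do not use relapse, so any inference that the primary test is compromised fails.

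The conclusion rests on the printed wording and on the assumption that the SAP's EFS and LFS entries, which are silent on the meaning of relapse, take it from Appendix A. The number of affected patients is unknown. The per-patient scale above assumes the planning CR rates. Nor do the documents show which reading, confirmation rule or event date is the intended one.

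**What to change.** Reconcile the passages under one definition:

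- In Appendix A, restate relapse as separate items for blood, marrow and extramedullary disease.
- State which finding, if any, needs a repeat marrow, how a patient without the repeat is classified, and which date is the event date. The sponsor must confirm the intended reading; this review does not choose it.
- In SAP 3.2, cross-reference that text for EFS, LFS, duration of morphologic CR and duration of composite CR. A cross-reference for EFS and LFS alone would leave the second definition in place.
- If a PD-based relapse definition is wanted for duration of CR, keep it deliberately and list it in SAP section 8 with the reason.

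The cost is wording in one appendix and cross-references in the SAP. Sample size and primary analysis do not change. If the confirmed rule calls for a repeat marrow, Tables 6-1 and 6-2 should show it, since neither does now.

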APPENDIX B – ECOG Performance Score

Grade	Description
0	Fully active, able to carry on all predisease performance without restriction
1	Restricted in physically strenuous activity but ambulatory and able to carry out work of a light or sedentary nature, e.g., light house work, office work
2	Ambulatory and capable of all self-care but unable to carry out any work activities. Up and about more than 50% of waking hours
3	Capable of only limited self-care, confined to bed or chair more than 50% of waking hours
4	Completely disabled. Cannot carry on any self-care. Totally confined to bed or chair
5	Dead

Source: As published in Am. J. Clin. Oncol. (CCT) 1982; 5:649-655.

APPENDIX C – Estimated Creatinine Clearance – Cockcroft Gault Formula

(As published in Nephron 1976; 16:31-41)

$$Cl_{cr} = \frac{(140 - \text{age}) \times \text{BM} \times \text{GF}}{S_{cr} \times 72}$$

BM = body mass (kg)

GF = gender correction factor (0.85 in females; 1.00 in males)

S_{cr} = serum creatinine (mg/dL)

APPENDIX D – Child-Turcotte-Pugh Classification of Severity of Cirrhosis

Parameter	Points Assigned		
	1	2	3
Ascites	Absent	Slight	Moderate
Bilirubin	<2 g/dL (<34.2 micromol/liter)	2 to 3 mg/dL (34.2 to 51.3 micromol/liter)	>3 mg/dL (>51.3 micromol/liter)
Albumin	>3.5 g/dL (35 g/liter)	2.8 to 3.5 g/dL (28 to 35 g/liter)	<2.8 g/dL (<28 g/liter)
Prothrombin time			
Seconds over control	<4	4 to 6	>6
INR	<1.7	1.7 to 2.3	>2.3
Encephalopathy	None	Grade 1 to 2	Grade 3 to 4

Source: website: www.uptodate.com, accessed 12 March 2015.

Modified Child-Turcotte-Pugh classification of the severity of liver disease according to the degree of ascites, the serum concentrations of bilirubin and albumin, the prothrombin time, and the degree of encephalopathy. A total Child-Turcotte-Pugh score of 5 to 6 is considered class A (well-compensated disease); 7 to 9 is class B (significant functional compromise); and 10 to 15 is class C (decompensated disease). These classes correlate with one- and two-year patient survival: class A: 100 and 85%; class B: 80 and 60%, and class C: 45 and 35%.

